4.3.2 Secondary outcomes

- Duration of stay due to pleural infection, as measured by the number of nights in hospital between enrolment and being recorded as medically fit for discharge
- Total inpatient time, as measured by the number of nights in hospital between enrolment and the end of the 90-day post-procedure follow-up period
- Need for step-up therapy, as measured by the difference in proportion of patients requiring intrapleural fibrinolytic therapy or referral for surgical debridement
- All-cause mortality, as measured by the number of patients remaining alive at days 30 and 90 post procedure
- Degree of pleural fluid septation, as measured by the change in bedside thoracic ultrasound septation score from baseline to follow-up days 1, 3, 7, 30 and 90 post procedure
- Pleural effusion size, as measured by the change in radiographic hemithorax opacification from enrolment to discharge, and days 1, 30 and 90 post procedure
- Microbiological yield, as measured by the difference in proportion with positive culture or stain between the control and intervention arms
- Total costs of interventions, as measured by the difference in total cost of treatment for pleural infection (from enrolment to being medically fit for discharge) between two arms
- Quality of life, as measured by the change in EQ-5D subjective health score from baseline to days 30 and 90 post procedure
- Patient experiences, as determined by exploring patients' perceptions and experiences of interventions before and after their procedure through semi-structured interviews

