6.3.4 Post-procedure inpatient period

Whilst an inpatient post-procedure, a patient's care will essentially follow standard practice. As such, on their first day post-procedure patients should undergo a clinical assessment, as well as a chest radiograph and blood tests (as detailed below). Further clinical assessments should then be made as per standard local clinical practice.

Blood tests should be performed on at least alternate days until day 9, and then at least weekly thereafter if the patient remains in hospital.

Thoracic ultrasounds should be performed on day 1 post procedure, and then on days 3 and 7 post procedure (+/- 1 day), and then every 7 days (+/- 1 day) if the patient remains in hospital.

The results of these, as well as the patient's symptoms (as measured by VAS scores) and clinical observations, will be recorded for trial purposes on days 1, 3 and 7 (+/- 1 day), and then every 7 days (+/- 1 day) until discharge or transfer to another hospital for ongoing care.

On day 7 post procedure (+/- 1 day), the patient should be asked to complete the EQ-5D health questionnaire. If the patient has been discharged, this should be completed at home and returned to the co-ordinating trial unit at Bristol.

The need for and timing of drain removal is at the discretion of the treating physician.

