7.1.3 Secondary endpoint analysis

Quantitative secondary endpoints will be analysed on both an intention-to-treat and, separately, a per protocol basis. Results will be presented in terms of between-group differences in either means or medians, with associated 95% confidence intervals.

Categorical data will be analysed using the Chi-squared approach (or Fisher's exact test where appropriate). Ordinal data will be analysed using the Mann Whitney U test or an independent sample t-test. Survival (time-to-event) data will be presented in the form of Kaplan-Meier curves and analysed using the Logrank test (with Cox proportional hazards analysis also performed).

The semi-structured interview component of the study will be analysed using a recognised qualitative approach, such as framework analysis, thematic analysis, or a combination of the two.

Analysis of anonymised radiological images will be performed by two clinicians, who will be blind to treatment allocation. Assessment of pleural effusion size will be performed using a recognised and previously published method. (7)

The comparison of treatment costs between randomisation and being medically fit for discharge will be performed from the perspective of the UK National Health Service, with prices of interventions or treatments being referenced from standard resources.

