9.3 RISKS AND ANTICIPATED BENEFITS FOR PARTICIPANTS & SOCIETY

Despite the SPIRIT trial being an investigation of feasibility, there are not expected to be any significant increased risks to individual participants over those associated with the standard clinical care of pleural infection. Both medical thoracoscopy and chest drain insertion are considered routine procedures in the management of patients with pleural effusions. Moreover, although the use of LAT is relatively rare for those with confirmed pleural infection in the UK, there are sufficient (albeit non-randomised) data to suggest that it may be undertaken safely by those with adequate experience. The primary potential benefit to those being randomised to the intervention arm in this study is a reduced duration of in-hospital treatment. Should this be supported by the trial’s results, it will enable a larger study to be performed looking to directly address this question, which may in turn lead to a wider, societal benefit in terms of improving the care pathway of those with pleural infection.

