APPENDIX 2 - TRIAL INTERVENTIONS SUMMARY TABLE

Timepoint	Events	Duration	Activities
Pre-enrolment	Screening and pre-screening	5 mins	Complete screening log for all patients with suspected pleural infection Provide patient information sheet where applicable
Enrolment	Trial consent	30 mins	Complete consent form A Provide patient information sheet B if participant agrees to semi-structured interview
Baseline assessment	Baseline assessment	60 mins	Baseline CRF EQ-5D questionnaire Thoracic ultrasound scan Bloods if not performed within previous 24 hours Chest x-ray if not performed within the previous two days
Randomisation	Randomisation and treatment allocation	10 mins	Access randomisation system and input required information Inform patient and necessary staff of treatment allocation
Intervention arm	Medical thoracoscopy on same or next day as need for drainage identified	90 mins	Appropriate procedural consent LAT (with pleural biopsies, maximal fluid drainage with samples, breakdown of immature septations, and pleural lavage with normal saline) Targeted 16F+ drain placement Fluid samples for M,C+S Chest radiograph within 12 hours of procedure end Research sample processing
Control arm	Chest drain insertion on same or next day as need for drainage identified	60 mins	Appropriate procedural consent Blunt dissection or Seldinger chest drain insertion of size $\geq 16F$ Fluid samples for M,C+S Chest radiograph within 12 hours of procedure end Research sample processing
Day 1 post procedure	Post procedure assessment	30 mins	Bloods Clinical assessment Thoracic ultrasound (if working day) Chest radiograph Day 1 post procedure CRF (including VAS)
Inpatient period	Inpatient assessments	30 mins each	At least alternate day bloods until day 9 post intervention (and at least every 7 days thereafter if remains in hospital) Thoracic ultrasound on days 3 (if working day) and 7 post intervention, and at least every 7 days thereafter if remains in hospital Clinical assessments as per local practice Days 3 and 7 post procedure CRFs and then extended stay CRF every 7 days until discharge (inc. VAS) EQ-5D day 7 post procedure Chest radiograph after drain removal (if occurs)
Discharge from admitting hospital	Discharge assessment	30 mins	Discharge CRF Arrange date for semi-structured interview if applicable

Timepoint	Events	Duration	Activities

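### The day 7 (and, less so, day 3) septation comparison depends on who is still in hospital, so it should be descriptive, and the ultrasound schedule should be reconciled

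*Protocol*

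**What the plan says.** Section 4.3.2 names the septation outcome as the "change in bedside thoracic ultrasound septation score from baseline to follow-up days 1, 3, 7, 30 and 90 post procedure". Section 7.1.3 analyses quantitative secondary endpoints by intention to treat and, separately, per protocol: "Results will be presented in terms of between-group differences in either means or medians, with associated 95% confidence intervals".

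The scan schedule appears in three places.

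- **Section 6.3.4** is headed as the post-procedure inpatient period and opens by limiting itself to that time. Results are recorded "on days 1, 3 and 7 (+/- 1 day), and then every 7 days (+/- 1 day) until discharge or transfer to another hospital". For the day 7 EQ-5D it adds a route for patients who have left: "If the patient has been discharged, this should be completed at home and returned to the co-ordinating trial unit at Bristol". It gives no such route for the scan.
- **Appendix 2** lists, in its inpatient row, "Thoracic ultrasound on days 3 (if working day) and 7 post intervention, and at least every 7 days thereafter if remains in hospital".
- **Section 6.5.1** asks for scan results on days 1, 3 and 7. Its in-hospital condition is attached only to the later weekly scans. It lets the day 1 or day 3 scan be missed outside working hours, provided at least one of the two is done.

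The first scheduled attendance after discharge is day 30 (section 6.3.8). On the expected effect of treatment, section 9.3 says: "The primary potential benefit to those being randomised to the intervention arm in this study is a reduced duration of in-hospital treatment".

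**The concern.** Being an inpatient on day 7 is an event after randomisation that the treatment may change. If only inpatients are scanned, the two arms are compared in subgroups that randomisation did not create. If thoracoscopy sends its better patients home sooner, its day 7 scores come from a sicker remainder, and a difference can appear, or a real benefit be hidden, through selection alone. Patients transferred elsewhere also drop out of recording, and they may differ from those who stay. A comparison restricted to those scanned would not be the intention-to-treat comparison that section 7.1.3 promises.

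The stakes are modest but real. Section 7.1.1 justifies 30 patients partly as enough to suggest differences between arms, and section 4.5 says the results should inform the design of a larger study. A distorted early septation signal could feed into that design.

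**Working it through.** **1. Does the schedule make day 7 scores depend on stay?** No sentence limits the scans to inpatients. The inference rests on five things taken together:

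- the heading and opening of section 6.3.4;
- recording "until discharge or transfer to another hospital for ongoing care";
- the inpatient row of Appendix 2;
- a home route for the EQ-5D but none for the scan, although discharge before day 7 is foreseen;
- no scan visit before day 30.

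Against it stands section 6.5.1, which read literally asks for day 3 and day 7 scans in everyone but provides no visit at which a discharged patient could have one.

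**2. Numbers per arm.** The protocol's own figure reproduces: 150 patients × 1/5 = 30. With 1:1 allocation that is about 15 per arm.

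**3. Size of the bias from early discharge.** The protocol gives neither day 7 discharge rates nor correlations, so these are assumptions:

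- no true effect on septation change, measured in SD units with higher meaning worse;
- the shortest stays leave before the scan, a proportion p in each arm;
- length of stay correlates r with septation change;
- nobody is lost by transfer.

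The mean among those scanned is r × φ(z_p)/(1 − p), where z_p is the normal quantile at p. Example with 30% of control and 60% of thoracoscopy patients discharged:

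- control: φ(−0.524)/0.7 = 0.3477/0.7 = 0.497
- thoracoscopy: φ(0.253)/0.4 = 0.3863/0.4 = 0.966
- difference: 0.966 − 0.497 = 0.469; with r = 0.5, 0.469 × 0.5 = 0.23 SD against thoracoscopy.

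The approximate 95% half-width is 1.96 × √(1/n₁ + 1/n₂). For 10.5 and 6 scanned it is 1.96 × √(0.0952 + 0.1667) = 1.00 SD.

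| Discharged before scan, control / thoracoscopy | r = 0.3 | r = 0.5 | r = 0.7 | Scanned, of 15 v 15 | 95% half-width |
|---|---|---|---|---|---|
| 10% / 30% | 0.09 | 0.15 | 0.21 | 13.5 v 10.5 | 0.81 |
| 20% / 50% | 0.13 | 0.22 | 0.31 | 12 v 7.5 | 0.91 |
| 30% / 60% | 0.14 | 0.23 | 0.33 | 10.5 v 6 | 1.00 |

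A simulation with 2,000,000 draws per arm agrees to two decimals. The bias is zero if r = 0 or if the arms discharge at the same rate. With all 15 v 15 scanned, the half-width would be 0.72 SD and this source of bias would be absent.

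**4. Which time points are affected?** Days 30 and 90 are scheduled attendances for every patient still in follow-up, and the early-discharge mechanism does not touch day 1. Day 3 is exposed in principle, but few discharges by then seem likely: section 2.1.1 describes long stays, and section 6.3.5 has enzyme therapy considered on the second day after the procedure.

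**The case against.** The strongest case against has four parts.

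*The text does not restrict the scans to inpatients.* A reader might infer from section 6.3.4 and Appendix 2 that discharged patients are definitely not scanned. The documents do not support that as a settled fact. In all three places the explicit in-hospital condition attaches grammatically to the later weekly scans, and section 6.5.1 has no inpatient framing. This stands, and it is why the point includes reconciling the passages. It does not remove the problem, because no visit exists to deliver a day 7 scan after discharge.

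*The protocol does not say that only observed scores will be compared.* Section 7.1.3 does not specify a complete-case analysis, and handling of missing data may sit in a statistical analysis plan not shown here. That is fair. But scores that the schedule does not collect can be replaced only by assumptions that the data cannot test.

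*The size is assumed.* Discharge rates and correlations have no source in the protocol, and a gap of 20 to 30 percentage points between arms is a large effect on stay. The outcome is a change from baseline, so severity that raises both scores alike cancels out; r could then be small, and the bias with it. This stands.

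*A reader might infer that the comparison is bound to go against thoracoscopy, or that day 3 is as badly affected as day 7.* Neither follows. Transfers are left out of the calculation and may act the other way; section 6.3.4 says only that they are for ongoing care, so how ill these patients are is not known. Day 3 is much less exposed, and its out-of-hours exemption is a separate source of gaps, probably unrelated to outcome.

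**Conclusion.** The concern holds for day 7 and, to a lesser degree, day 3. As scheduled, the day 7 between-group difference is open to selection on length of stay, a consequence of treatment. Under the assumptions above, early discharge alone gives roughly 0.1 to 0.3 SD against thoracoscopy, at most about a third of the confidence interval half-width of about 0.8 to 1.0 SD (for example 0.33/1.00). The net direction, with transfers included, is uncertain. This concerns one secondary outcome in a 30-patient feasibility trial. The primary feasibility outcome and its success thresholds in section 7.1.2 are unaffected. The change is worth making because it costs little, not because the trial's main conclusion is at risk.

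**What to change.** - In sections 4.3.2 and 7.1.3, rest the between-arm septation comparison on day 30, with day 90 supportive. Keep day 1 as the early comparison, noting that the out-of-hours exemption will leave some gaps.
- Report days 3 and 7 descriptively by arm, with the numbers in hospital, discharged, transferred and scanned, and without a between-arm test.
- Reconcile sections 6.3.4, 6.5.1 and Appendix 2 so that they say the same thing about whether discharged patients are scanned on days 3 and 7.
- Report numbers scanned at days 30 and 90 as well: section 6.3.8 allows telephone or notes-based follow-up for patients who do not attend, which yields no scan.

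This fits the rest of section 4.3.2: the EQ-5D outcome is already set at days 30 and 90 although a day 7 questionnaire is collected, and effusion size omits days 3 and 7. The cost is wording only, with no new scans or visits. The downside is the loss of a formal day 3 or day 7 contrast.

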4.4 FUNDING

The SPIRIT trial is supported by a Starter Grant for Clinical Lecturers awarded to the Chief Investigator by the Academy of Medical Sciences.

4.5 TRIAL DESIGN JUSTIFICATION

- As mentioned above, the role of medical thoracoscopy in the management of pleural infection is largely unexplored. Theoretically, this intervention may have a place at any stage, ranging from first fluid drainage through to using it as a tool to try to avoid surgery in those who have failed first-line drainage, or even as an alternative to more invasive VATS procedures in those with persistent non-resolving disease. This study has chosen to focus on the former, and examines whether using medical thoracoscopy as the first intervention in pleural infection is feasible and acceptable. The primary rationale for this is minimising the demand for UK thoracoscopists to undertake procedures outside of their typical experience, which lies in the management of collections which should theoretically respond to standard drainage.
- SPIRIT is a feasibility study as opposed to a pilot study, which means the information it is able to generate will hopefully be used to *inform the design* of a larger study examining the efficacy of LAT in the pleural effusion population, rather than being a smaller but fixed template for such a study.
- The decision to target a relatively selected pleural infection cohort for randomisation has been carefully considered. It would be possible to design the SPIRIT trial to include and randomise all pleural infection patients needing drainage regardless of day or time of presentation, or indeed of 'suitability' for LAT, and then analyse them on an intention-to-treat basis to determine the 'real-world' impact of using LAT in this population. This approach would theoretically minimise selection bias. However, given that very few (if any) UK centres are currently set up to perform urgent thoracoscopy, and not all investigators would be comfortable performing LAT in a completely unselected population, this approach would likely place investigators in the situation of having to consent patients to potentially being randomised to a treatment arm they know they will not be able to deliver. Aside from the ethical issues this may raise, it would likely also lead to a significant number of allocation failures in the LAT arm and would thus blunt the ability to interpret any data based on comparisons with this group.
- The trial will therefore only look to enrol those patients who are felt to be suitable for a LAT, and can also have one performed if that procedure is assigned. However, understanding as complete a picture as possible of the population from which trial participants are drawn is considered vital to the design of any future studies. As such,

robust pre-screening and screening data will be collected alongside those regarding enrolled patients, and this will form part of the analysis and discussion of SPiRiT.

5. PARTICIPANT ENTRY

5.1 PRE-SCREENING AND SCREENING

Potential trial participants will be identified by clinical members of staff at participating recruitment centres, and may be drawn from acute respiratory and general medical services, as well as from ward referral and outpatient pathways. Electronic logs will be kept maintaining details of all patients who are pre-screened and screened, as defined below.

5.1.1 Pre-screening

All patients who have a suspected infected pleural effusion, based on radiological findings and routine clinical assessment by an appropriate specialist, should be entered onto the pre-screening log (“pre-screened” patients). All pre-screened patients should be assessed against the inclusion and exclusion criteria, detailed below. Those who are ineligible for trial entry should have the reasons for this entered on the log, and will be deemed to be “pre-screen failures”. Patients may be entered onto the pre-screening log retrospectively, but only if they presented with suspected pleural infection during the trial recruitment period.

5.1.2 Screening

Those who meet the trial inclusion and exclusion criteria should be entered onto the screening log and offered a patient information sheet (“screened patients.”). Those patients who do not proceed to trial enrolment should be recorded as “screen failures,” with the reason for this documented on the screening log. If a patient deteriorates clinically while they are considering trial entry such that they require urgent chest drainage before they are enrolled, they should also be recorded as a screen failure.

As per the inclusion criteria below, patients must undergo drainage on either the same or next day as they are diagnosed as needing drainage. Therefore, if a patient wishes to consider trial entry overnight, the trial team must be able to perform the allocated procedure on the *same* day as enrolment and randomisation.

5.2 INCLUSION CRITERIA

1. Suspected pleural infection, defined as an effusion (in the appropriate clinical context) with one or more of the following characteristics:

- a. Fluid pH ≤ 7.20 or visually contains pus
 - b. Pleural fluid glucose ≤ 3.4 mmol/L
 - c. Positive bacterial or mycobacterial culture
 - d. Positive gram stain or stain for acid-fast bacilli
2. Clinical team expect to be able to perform a medical thoracoscopy, if allocated, on either the same or the next day as the effusion is diagnosed as requiring drainage
 3. Clinical team expect to be able to deliver the post-procedure trial schedule as detailed in the protocol

5.3 EXCLUSION CRITERIA

1. Any contraindication, in the opinion of the trial team or lead clinician, to
 - a. Medical thoracoscopy performed under conscious sedation
 - b. Chest drain insertion
 - c. Patient trial involvement
2. Research team unable to obtain, or patient unable/unwilling to provide, informed consent to trial participation
3. Thoracic imaging demonstrating fluid septation, loculation or position which would render medical thoracoscopy or standard medical management alone inappropriate, in the opinion of the trial team or lead clinician
4. Maximum pleural fluid depth of ≤ 2 cm on thoracic ultrasound
5. Ongoing sepsis requiring haemodynamic support beyond basic fluid resuscitation
6. Previous pneumonectomy or lobectomy on the side of the effusion (or any ipsilateral thoracic surgery within six months)
7. Age < 18
8. Pregnancy or lactation
9. Expected survival ≤ 3 months

5.4 WITHDRAWAL CRITERIA

Patients in the trial will have consented to randomisation and trial follow-up. Patients have the right to withdraw from the trial at any point. Withdrawal does not have to be justified and will not affect future or ongoing care. In the event of withdrawal, any details available for the reason(s) should be

recorded, and clarification on the nature of the withdrawal of consent, as outlined below, should be sought. At the discretion of the Principal Investigator, patients may be withdrawn if it is felt to be appropriate or in their best interest to do so. Patients may still be stratified as 'alive' or 'dead' at the end of their follow-up period, unless consent for clinical data use is withdrawn. Available data from patients withdrawn following randomisation will be included intention to treat analyses unless patients withdraw permission for use of this data.

5.5 CO-ENROLMENT GUIDELINES

Patients may only undergo randomisation as part of the SPIRIT trial once. Patients who enrol but are withdrawn before randomisation may be re-enrolled as a new participant.

Patients should not be enrolled if they are participating in another interventional study relating to pleural infection. Participation in other clinical trials will not be limited, however there should be discussion between the relevant teams prior to enrolment to ensure compatibility between protocols, as well as with the patient to ensure they are happy to be involved in multiple studies.

